6 STUDY INTERVENTION(S) OR EXPERIMENTAL MANIPULATION(S)

6.1 STUDY INTERVENTION(S) OR EXPERIMENTAL MANIPULATION(S) ADMINISTRATION

6.1.1 STUDY INTERVENTION OR EXPERIMENTAL MANIPULATION DESCRIPTION

The *EndeavorRx* video game is a digital therapeutic designed to improve attention and related cognitive control processes by training interference management. The video game design displays two tasks that are to be completed in parallel, which requires multitasking and thus cognitive control. Task performance is assessed during single and interference (multitask) conditions. Difficulty of the game is titrated, in real time, to adapt to the individual's performance. The game-player makes progress by earning rewards and thus unlocking new environments. Periodic recalibration occurs throughout gameplay to maintain an optimal difficulty level. This feature of the game helps to avoid participant boredom and progressively activate the functional systems underlying cognitive control. *EndeavorRx* is similar to other cognitive training intervention games used in prior research and are well-tolerated by participants of varying ages (Keefe et al., 2022).

6.1.2 ADMINISTRATION AND/OR DOSING

Computerized cognitive training: The CCT intervention will consist of ~25 minutes of EndeavorRx video gameplay per day (at any time of the day), for 5 days/week, for 4 weeks. This is the duration of gameplay used in prior studies of the *EndeavorRx* game (Kollins et al., 2020) and the dose suggested by *Akili Interactive*. Participants will be instructed to try not to play the game for more than 30 minutes a day, though time of gameplay will be monitored directly by the research team using Akili software. If participants are playing the video game too much, or for not enough time, parents will be contacted via email. The video game is designed to improve attention and engage cognitive control. Gameplay sessions will be completed at home. Participants will complete CCT on an iPad provided by the research team, or they may complete CCT by downloading the *Akili Interactive* application onto their own Akili-compatible personal device.

6.2 FIDELITY

6.2.1 INTERVENTIONIST TRAINING AND TRACKING

An evaluator will assess the patients with the scales described below. The assessments will be completed via Zoom.

To ensure that there is consistency across participants in understanding of gameplay instructions, participants will be instructed to play the CCT intervention for about 5 minutes while the coordinator monitors the session over Zoom. The research coordinator will then be able to answer any questions that the participant might have about game instructions. All participants will also be provided with the same instruction manual.

6.3 MEASURES TO MINIMIZE BIAS: RANDOMIZATION AND BLINDING

There is no randomization in this pilot study.

6.4 STUDY INTERVENTION/EXPERIMENTAL MANIPULATION ADHERENCE

Tolerability and compliance with the intervention will also be assessed. The CCT application will measure the amount of time each day that the child spends playing the video game. Additionally, completion of self-report questionnaires and *Millisecond* assessments will be tracked to ensure that these assessments are completed within the specified time period. If the cognitive task battery and start of the cognitive training intervention are not completed within sufficient time of the baseline clinical and self-report assessment (i.e., within 14 days of completing the CDI; due to scheduling and/or equipment constraints), then the CDI and CDRS-R will be re-administered prior to initiating the cognitive task battery and cognitive training.

Assessments will include (refer to 1.3 Schedule of Activities for a list of which measures are completed at each assessment):

Assessments by Clinician

- a) C-SRSS
- b) CDRS-R
- c) K-SADS

Assessments Completed by Subjects

- a) MASC
- b) CDI
- c) SCARED (parent)
- d) CBCL (parent)
- e) ERQ-CA

Other Assessments

- a) ESS (parent and child)

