1.3 SCHEDULE OF ACTIVITIES

	Pre-screening (Pre-consent)	Assessment 1 Day 1	Assessment 2 Day 60±30	Assessment 3** 150±20
Review eligibility with phone screen	X			
Informed Consent		X		
Demographics		X		
Clinical assessment				
CBCL		X		
MASC		X	X	X
CDI		X*	X	X
K-SADS (Clinical report)		X		
SCARED-P		X		X
CDSRS		X*	X	X
C-SSRS		X		
ERQ-CA		X	X	X
Behavioral assessment				
Millisecond Inquisit Web Cognitive Battery		X	X	X***
Other assessments				
ESS			X	X
Adherence Metrics from Akili			X	X
Debrief				X
Adverse Events Reporting		X	X	X

*These assessments may be administered more than once if >14 days pass before the cognitive battery and cognitive training can be administered. See Section 6.4 for additional details.

**Assessment 3 was optional to participants and then discontinued in protocol version 2.1 (02 April 2024).

***Provided iPads will be re-collected after Assessment 2. If participants do not have access to a personal tablet from which they can complete the tasks from, then they will not complete the Cognitive Battery at Assessment 3 (if applicable).

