Depressive symptoms may worsen during the course of the participation in the study, including the emergence of suicidality. During the screening period in Assessment 1, suicidal thoughts, plans, intentions and behaviors will be assessed with the Columbia-Suicide Severity Rating Scale – Screen Version (C-SSRS). If assessment uncovers suicidal plans or intentions or recent behaviors, emergency evaluation will occur, and an appropriate plan of action will be followed, e.g. safety plan will be created and referral to psychiatric emergency room. Subjects will not continue to be enrolled in the study if any items on the C-SSRS are endorsed during the screening period of Assessment 1. Therefore, any potential participant with suicidal thoughts or behaviors will be excluded from the study. Suicidal thoughts will also be assessed after the 4-week intervention and (if applicable) at a 3-month follow up through items on the CDI and CDSRS. If these items are endorsed, then evaluation will occur, followed by an appropriate plan of action (as stated above). If symptoms worsen during the course of participation, but not to the level of suicidal thoughts, plans, intentions or behaviors, the participant may be withdrawn (see 7.1 below).

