5 STUDY POPULATION

5.1 INCLUSION CRITERIA

In order to be eligible to participate in this study, an individual must meet the following criteria:

1. Parent or guardian willing to give informed consent, and children willing to give informed assent to participate in the study.
2. Males and females (age 9 – 17.99)
3. Participant is willing to engage in a technology-based intervention (technology will be provided to participants who live in the state of Michigan, if not already accessible to participant).
4. Self-reported depressive symptoms (CDI score between 3-19 at Assessment 1)
5. Participants will be required to maintain a stable dose of medications for 4 weeks prior to the first assessment and stable medication throughout the intervention period. Participants may change medication after completion of the post-intervention assessment (i.e. in between the post-intervention assessment and follow-up assessment).

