5.2 EXCLUSION CRITERIA

An individual who meets any of the following criteria will be excluded from participation in this study:

An individual who meets the following criteria will be excluded from participation in this study:

1. Color blindness
2. Unable to play the video game for any reason
3. K-SADS diagnosis of clinical depression, psychosis, or Autism Spectrum Disorder
4. Has enrolled in new psychotherapy (for the treatment of a mood or anxiety disorder) or had changes to their psychotherapy in the 4-weeks prior to study enrollment
5. Endorses items #1, #2, #3, #4, #5, #6 on the C-SSRS Screener (Past-Month); i.e., has present suicidal intention/behavior.
6. Has had any changes to their medication in the 4-weeks prior to study enrollment

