5.4 SCREEN FAILURES

Screen failures are defined as participants who consent to participate in this study but are not subsequently assigned to the study intervention or entered in the study. Individuals who do not meet the criteria for participation in this trial (screen failure) because of meeting one or more exclusion criteria that are likely to change over time may be rescreened. Rescreened participants will be assigned the same participant number as for the initial screening.

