7.1 DISCONTINUATION OF STUDY INTERVENTION/EXPERIMENTAL MANIPULATION

When a subject discontinues from CCT but not from the study, remaining study procedures will be completed as indicated by the study protocol. If a clinically significant finding is identified (including, but not limited to changes from baseline) after enrollment, the investigator or qualified designee will determine if any change in participant management is needed.

Discontinuation of study for a given participant will occur in the event of any of the following:

- Suicidal thoughts with specific plans and intentions (Endorse item 9 the CDI)
- The participant is hospitalized for any psychiatric symptoms
- A participant reports symptom worsening: > 25% increased CDI score (referenced to baseline)

Reasons for discontinuation will be documented, and all outcome assessments will proceed as scheduled, if possible.

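### When training starts more than 14 days after the CDI, the CDI and CDRS-R are repeated but the past-month C-SSRS that defines exclusion 5 is not

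*Combined protocol and SAP*

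**What the plan says.** Section 6.4 expects the cognitive battery and the start of training to follow within 14 days of the CDI. If they do not, "then the CDI and CDRS-R will be re-administered prior to initiating the cognitive task battery and cognitive training". The footnote to the schedule in 1.3 is more permissive: "These assessments may be administered more than once if >14 days pass before the cognitive battery and cognitive training can be administered". Its asterisk stands on two rows only, CDI and CDSRS, in the Assessment 1 column. (CDSRS is taken here to be the CDRS-R under another abbreviation.) The C-SSRS row has a plain mark at Assessment 1 and none later.

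Exclusion 5 in section 5.2 is written on the C-SSRS: "Endorses items #1, #2, #3, #4, #5, #6 on the C-SSRS Screener (Past-Month". Section 2.3.1 adds that enrollment does not continue "if any items on the C-SSRS are endorsed during the screening period of Assessment 1". Sections 8.1 and 8.2 also tie the instrument to Assessment 1.

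After screening, the protocol looks for suicidal thoughts with other instruments. Section 2.3.1 assesses them after the intervention and, where applicable, "at a 3-month follow up through items on the CDI and CDSRS".

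**The concern.** By its own 14-day rule, the protocol treats a CDI older than two weeks as too old to start from. The C-SSRS belongs to the same assessment and has a stated recall period of one month, and exclusion 5 depends on it alone. Section 8.1 also relies on it for the assurance that a dangerous condition is found before a child starts the intervention. Yet it is the one suicidality instrument that the delay rule leaves out.

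The stake is participant safety in 9- to 17-year-olds with depressive symptoms. Any endorsed C-SSRS item keeps a child out at entry. A child in whom ideation appears between Assessment 1 and a delayed start would not meet that same test again. Estimation is not at stake.

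**Working it through.** The plan gives no figure on this point, so the check sets the sections side by side.

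1. **What defines the suicidality exclusion?** Items 1 to 6 of the past-month C-SSRS (5.2, exclusion 5). No other instrument is named in that criterion.

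2. **What is repeated after a delay?** The CDI and CDRS-R (6.4, and the asterisks in 1.3). The C-SSRS is in neither place. No section maps a CDI or CDRS-R answer to exclusion 5, so the repeat as written does not reapply that criterion.

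3. **Can the delay be long?** Assessment 2 is at Day 60 ± 30, with Assessment 1 on Day 1 (1.3), and training lasts 4 weeks = 4 × 7 = 28 days (6.1.2). The latest start is the Assessment 2 day minus 28.
   - At the nominal Day 60: 60 − 28 = Day 32, which is 31 days after Day 1.
   - At the window's upper end, Day 90: 90 − 28 = Day 62, which is 61 days after Day 1.

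   This assumes that the C-SSRS is done on Day 1 and that Assessment 2 directly follows training. The visit windows therefore do not hold the delay close to 14 days. These figures give the possible age of the C-SSRS. They do not measure time without any suicidality check, because the CDI and CDRS-R are repeated before the start.

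4. **What else would catch new ideation before training?**
   - The repeated CDRS-R is a clinician-administered interview (8.1) with suicidality items (2.3.1). No section says which answer prevents a start.
   - Ideation endorsed on the CDI at any point is flagged, and the team acts on it (8.1). Qualtrics is reviewed at least weekly (10.1.7).
   - Endorsing CDI item 9 leads to discontinuation, and the wording is mandatory (7.1).
   - Any potential participant with suicidal thoughts or behaviors is to be excluded (2.3.1). The sentence follows from the C-SSRS screen but is worded generally.
   - The investigator may discontinue a child who newly meets an exclusion criterion (7.2). This is discretionary.

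5. **What is left?** These provisions give substantial cover against ideation going unnoticed. The remainder is narrow: exclusion 5, as defined on the C-SSRS, is not rechecked for a delayed child.

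**The case against.** The strongest case against the point is that a delayed child is looked at more closely at the start of training than a child who begins on time. The delayed child has an extra CDI and an extra clinician interview just beforehand; the on-time child has neither. The repeated instruments are also the pair the protocol chose for detecting suicidal thoughts after screening. An ageing C-SSRS is not peculiar to delayed children either: a child who starts at 14 days ends training with a C-SSRS that is 14 + 28 = 42 days old. All of this stands, and it is why the gap is small. It does not explain why an entry assessment is refreshed after 14 days without the scale on which the suicidality exclusion is written.

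Three stronger readings are tempting, and the documents do not support them.

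- A reader might infer that the protocol leaves open which CDI governs entry. Section 5.1 asks for "Self-reported depressive symptoms (CDI score between 3-19 at Assessment 1", and the repeat asterisk is in the Assessment 1 column. The natural reading is that the range covers the repeat. At most, a clarifying detail is missing.
- A reader might infer that a repeat CDI above 19 is a safety hole when it does not also meet the 7.1 rule, "A participant reports symptom worsening: > 25% increased CDI score (referenced to baseline". Nineteen is an entry ceiling. No section calls a score just above it unsafe, and clinical depression is excluded by the K-SADS.
- A reader might infer that the days not covered by the C-SSRS recall period are days without suicidality screening. That ignores the repeated CDI and CDRS-R.

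**Conclusion.** The point holds as a small safety gap and an inexpensive improvement, not as an error in the plan. After a delay of more than 14 days, a child may start training without exclusion 5 being rechecked, because the C-SSRS is outside the repeat. Other provisions would probably bring new ideation to the team's attention, so severity is low. The conclusion rests on reading CDSRS and CDRS-R as one instrument and on taking the 6.4 list and the 1.3 asterisks as complete. The documents do not say how many children will be delayed, so the number affected cannot be estimated.

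**What to change.** Add the C-SSRS to the asterisked rows in 1.3 and to the repeat list in 6.4, and say what is done with the result. For example: *If training has not begun within 14 days of the CDI, the past-month C-SSRS is repeated together with the CDI and CDRS-R. Exclusion criterion 5 is reapplied to the repeat C-SSRS before the first training session, and a child who endorses any item does not start.*

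The change should stop there. Rechecking all of 5.2 would need another K-SADS, which takes 3 to 4 hours (8.1). Reapplying the CDI floor of 3 would remove children who have improved, with no safety reason.

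The C-SSRS takes about 5 minutes (8.1). Section 6.4 lists it with the CDRS-R as a clinician assessment, so it fits the contact that already takes place. If all 30 planned children were delayed, the total would be 30 × 5 = 150 minutes. The other cost is possibly a few exclusions after the K-SADS has been done, in a study where recruitment is already a constraint (9.2). Such children fit the screen-failure definition in 5.4, "participants who consent to participate in this study but are not subsequently assigned to the study intervention or entered in the study", and may be replaced under 7.2.

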6.5 CONCOMITANT THERAPY

Participants can remain on medication throughout the duration of the study, so long as a stable dose was maintained at least 4 weeks prior to study enrollment, and that this dose is maintained throughout the study's duration. Participants will be excused from the study if they decide to seek new therapy or medication during the course of the study.

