5.3 LIFESTYLE CONSIDERATIONS

Participants must maintain stable doses of any medication throughout participation in this study. Initiation of new medications, or substantial changes in dosage of current medications, prior to the end of the study, may be requested by the patient. In this event, the patient will be withdrawn from the study and referred to clinical care.

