2. After completing one half of the CCT training (2 weeks), participants will *earn* an additional \$25.
3. Once the full training has been completed (4 weeks of at least 80% compliance), participants will *earn* another \$25.
4. *After completing Assessment #2, participants will *earn* another \$25.
5. **For those who have completed Assessment #3 3-months post-intervention, participants earn an additional \$25.

Therefore, if all three assessments are completed in addition to the full EndeavorRx intervention, each participant will receive a total of \$150. All participants will have the opportunity to earn the same amount of compensation (if completed Assessment #3). Incentives are structured to promote retention of participants throughout the full intervention period, as well as for Assessment #3 (if applicable). Payment for all enrolled participants will be made in up to two payments: at payment step #4* and again at payment step #5**, if all activities completed. If participants screen out during Assessment 1, they will be provided payment after screening out. The participant will receive the incentive directly. If a participant withdraws from the study or does not complete certain parts of the study, payment will be distributed for the amount earned at the point of study discontinuation. If a participant does not complete at least 2 weeks of the CCT intervention, they will not complete the post-intervention assessments.

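### No final CDI is secured for children withdrawn for new treatment, so the complete-case change leans towards benefit if they leave because they are worsening (minor)

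*Combined protocol and SAP*

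**What the plan says.** Two sections remove a child for new treatment. Section 6.5 states: "Participants will be excused from the study if they decide to seek new therapy or medication during the course of the study". Section 5.3, on new medication or a substantial dose change, states: "In this event, the patient will be withdrawn from the study and referred to clinical care". Section 7.2 also lets the investigator discontinue a child whose situation may call for other treatment that would cloud interpretation. None of the three mentions a last CDI or Assessment 2.

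Section 7.1 has a retention sentence: "Reasons for discontinuation will be documented, and all outcome assessments will proceed as scheduled, if possible". Its listed triggers are suicidality, psychiatric hospitalisation and "A participant reports symptom worsening: > 25% increased CDI score (referenced to baseline"). Section 2.3.1 points worsening without suicidality to the same place: "the participant may be withdrawn (see 7.1 below").

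Section 7.2 records the reason for withdrawal and replaces children who leave after receiving the intervention. Section 5.5 adds: "If a participant does not complete at least 2 weeks of the CCT intervention, they will not complete the post-intervention assessments". Section 9.3 defines the complete-case population by having the Assessment 2 data, 9.4.1 applies listwise deletion, and 9.4.2 tests the CDI with a paired t-test. No sensitivity analysis for missing Assessment 2 data is planned.

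**The concern.** The protocol itself links worsening to exit. Section 6.5.1 refers a child whose depression worsens to therapy, including on spontaneous report. Section 6.5 then excuses a child who decides to seek it. If that happens before Assessment 2, the score most likely to show harm may never be collected, and the child is replaced and left out of the test.

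Two results would be affected: the pre-post CDI change, with the effect size that 9.2 intends for later studies, and the 9.4.6 check for worse CDI at Time 2, which sees only children who have a Time 2 score.

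**Working it through.** **Step 1: follow one child through the rules.** A child worsens in week 3 and the family asks for therapy.

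- 6.5.1 refers the child and 6.5 excuses the child.
- 7.2 records the reason and replaces the child.
- 7.1 does not list new treatment. Its CDI trigger needs a CDI, and none is scheduled in this window. Section 1.3 allows repeats only before training: "These assessments may be administered more than once if >14 days pass before the cognitive battery and cognitive training can be administered". The next CDI is Assessment 2, at day 60±30, that is, days 30 to 90.
- If less than two weeks of training was done, 5.5 rules out the post-intervention assessment.
- 9.3 and 9.4.1 leave the child out.

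**Step 2: the plan's own figure.** Section 9.2 gives 32 children for 80% power, without an effect size or SD. The normal approximation with a standardised change of 0.50 gives ((1.960 + 0.842)/0.50)² = 31.4, so 32. That is consistent with the plan but cannot be confirmed. The documents give no SD of change and no exit rate, so all inputs below are assumptions. An SD of 5 points and a change of 2.5 points give 2.5/5 = 0.50.

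**Step 3: simple arithmetic.** Error in the complete-case mean = −(k/N) × (leavers' mean change − stayers' mean change), with N = 30. Leavers are assumed to change by +2 to +5 points and stayers by 0 to −2, so the difference in brackets is 2 to 7.

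- k = 1: 2/30 to 7/30 = 0.07 to 0.23 points too favourable
- k = 3: 6/30 to 21/30 = 0.20 to 0.70
- k = 5: 10/30 to 35/30 = 0.33 to 1.17

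**Step 4: false finding of a reduction, no true effect.** Simulation with 40,000 trials per cell and n = 30. Early worsening e is N(0,1). Final change = 5 × (ρe + √(1−ρ²)u), with ρ = 0.5 or 0.7. Exit is logistic in e with slope 1 or 2, calibrated to the stated proportion. The test is a paired t-test with 2.5% in the lower tail. Full credit means that leavers enter with an Assessment 2 score taken after new treatment has lowered their CDI by 2.5 or 4 points.

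| Leaving | Plan as written | Full credit, 2.5 points | Full credit, 4 points |
|---|---|---|---|
| 1 of 30 | about 3-4% | – | – |
| 10% | 4.3-7.3% | 4.5-4.7% | 6.3-6.4% |
| 20% | 6.2-14.7% | 7.6-8.0% | 13.1-14.9% |
| 10-20%, unrelated to e | 2.4-2.5% | – | – |

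The mean change under the plan at 10-20% leaving is −0.2 to −0.9 points. Replacing leavers up to 30 completers does not repair this (4.3-17.4%). A simpler model, in which k randomly chosen worseners leave, gives 3.8% (k = 1), 5.5% (2), 7.6% (3) and 14.5% (5).

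**Step 5: the 9.4.6 check.** Suppose training truly raised the CDI by 2.5 points. The chance that the CDI comparison finds significant worsening is about 75% with all scores, 69-72% with 1 of 30 missing and 36-63% with 10-20% missing. Section 9.4.6 also has a withdrawal limit. If seven withdrawals coded as due to symptoms count as reaching it, the combined chance at 20% leaving is 62-72%. If more than 10 of 30 are needed (30/3 = 10), it is 37-52%.

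**The case against.** **Removal is deliberate.** Medication is held stable until the post-intervention visit (5.1: "Participants may change medication after completion of the post-intervention assessment"), and 7.2 gives confounding treatment as a ground for discontinuation. That stands, and the withdrawal rule is not criticised here. It does not prevent taking one last score before the new treatment begins.

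**Worsening children are partly covered.** Section 2.3.1 sends them to 7.1, and 7.1 tries to keep their outcomes. That also stands, and it narrows the gap to children handled only under 5.3, 6.5 or the 7.2 clause who leave before Assessment 2. Read generously, the 7.1 sentence might reach them too, but it promises no more than an attempt.

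**Losses are visible.** A reader might infer that three to six such exits would go unseen. The documents do not support that. Section 7.2 records every reason, 8.2 makes a missed Assessment 2 CDI a reportable deviation, and the team meets biweekly (10.1.6). What is true is narrower: that number would not reach the 9.4.6 halting limit, whether taken as about seven children or as one third, and recording an exit does not supply the missing score.

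**The size is speculative.** This stands in full. The larger figures need three to six exits driven by worsening, and no figure in the documents supports that number.

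**Conclusion.** The gap is real and minor. For children withdrawn for new treatment, no rule secures a final CDI, and the analysis then drops them. If exits follow worsening, the direction is towards benefit. The size is unknown: small at 1 of 30 (about 3-4% against 2.5%), larger only under assumed exit rates of 10-20%, and without inflation if exits are unrelated to mood. The figures rest on an assumed SD of 5 points, an assumed correlation and an assumed exit mechanism.

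A reader might go further and conclude that the trial's CDI result will be biased, or that this is a main limitation. The documents do not support either: they give no exit rate, some treatment changes will have nothing to do with mood, and the lack of a control group is the larger threat to a pre-post change.

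**What to change.** Keep the stability and withdrawal rules, and make these changes:

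1. In 5.3, 6.5 and 7.2, state that the CDI (and the CDRS-R where feasible) is obtained at withdrawal, before new treatment starts where possible. This is practical because the trigger in 6.5 is the decision to seek treatment.
2. In 5.5, exempt this exit assessment from the two-week training rule.
3. In 9.3, state that CDI scores obtained after new treatment starts do not enter the planned complete-case test. Otherwise a child followed to Assessment 2 on new treatment becomes a complete case, and the planned test turns into the full-credit analysis in the table, which can be worse than the present plan.
4. Report how many children left for this reason and when.
5. Give one supporting analysis of CDI change that includes the exit scores, and use it for the 9.4.6 check as well.

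The cost is a few sentences, a few short remote assessments (8.1 puts the CDI at about five minutes and the CDRS-R at 15-20) and one extra analysis. The exit-score analysis leans somewhat against benefit when children leave at a low point, by about 0.1 to 0.35 points in a simulation with assumed inputs. It should therefore stand beside the planned test, not replace it.
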